- a) P&E Intervention Participants will be eligible to participate if they: 1) are students at the selected schools, 2) self-identify as lesbian, gay, bisexual, transgender, or any other non-heterosexual/cisgender identity, 3) speak English, and 4) are able and willing to provide assent/consent.
- b) POL Allies/Make Space Participants will be eligible to participate if they: 1) are selected by P&E intervention participants as a popular opinion leader (i.e. students who others look up to and consider good leaders), 2) are willing to be an ally to the LGBTQ community, and 3) are able and willing to provide assent/consent.
- 2. Exclusion Criteria: not meeting the inclusion criteria above

3. Special Population:

- a) Minors: a waiver of parental permission for youth participation has been granted as there is concern that an IRB requirement of parental permission will put some sexual minority youth at risk regarding disclosure of their sexual orientation to their parents. This may then place these youth at risk for parental harassment, abuse, or expulsion from the parental home.
- b) Pregnant Women: There is no risk to pregnant individuals due to participation. Therefore, we will allow those who are pregnant to participate in the study.

4. Limitations:

- a) Although our feasibility trial had one school with 17 youth participating in the Proud groups, we found that this group was too large to manage effectively, and so we will limit the individual-level intervention group size to 12.
- b) Given that this is a Los Angeles-based study with a limited budget and that the majority of schools in the Greater Los Angeles Area are English speaking, we will be restricting enrollment those who speak English.

Recruitment

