participate in the intervention session. Schools will choose what works best for them. If option 2 is selected, intervention sessions will be staggered and run during a different class period each week so that participating youth do not miss the same class every week. Study staff ([name]) will present adolescents with information sheets/assent, or informed consent from those aged 18 or older, and obtain assent/consent in order to keep as little identifying information about LGBTQ+ participants as possible. Next, each LGBTQ participant will create a unique identification code that will be used in the participant's survey entries to link successive data points. Surveys will be self-administered on tablets, laptops, or cell phones. The data manager and study facilitator at the study site will track participant names and unique identifiers to keep track of the number of sessions attended by students (dosage). School staff will not have access to participant data from surveys. Youth who turn 18 during the study will complete an informed consent.

10-week P&E Intervention Procedures: A PDF of the Proud & Empowered intervention program can be found in the attachments section of this IRB application as "Proud & Empowered.pdf". The 10-week protocol includes an introductory and data collection session, then sessions on Stress and Coping, Disclosure, Families, Peers and Friendship, School-related Stress, Spirituality/Religion, Social Justice, Health and Wellness, and a final Celebration and data collection session. Each session runs about 45 minutes and will be Facilitated by MSW-level study staff. We have formalized the process for tracking fidelity and other outcomes after each session via a post-session facilitator feedback form. This form (uploaded to "attachments" section as "Post-Session Data Collection.docx) will be completed by the intervention facilitator ([name]) immediately after each session. Data to collect includes attendance (dosage), intervention location, and information on participant engagement and collaboration.

School Policy Scan

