Additional protocol for identifying suicidality in survey participants: Because the intervention participant surveys assess for recent suicidal ideation, intent, plans, and attempts, we will implement protocols to immediately identify youth who report suicidal risk and connect them to the school counselor. The participant survey will be programmed in Qualtrics and the final screen for all youth will instruct them to: "Let the research team know you've finished the survey to receive your gift card. Code: complete." This will allow the team to verify survey completion and give the student their gift card. The Qualtrics survey will be programmed to include the youth's score on the suicide measures with the "Code: complete" message, such that students with no risk will get "Code: complete 1" and those with highest risk will get "Code: complete 5." This code is designed to not catch the attention of the student, but still allow the research staff to note the student's risk level, and then confidentially connect the student to the school counselor for further help outside of the intervention session.

References:

- 2. D'Augelli A, Grossman, Arnold H. Disclosure of sexual orientation, victimization, and mental health among lesbian, gay, and bisexual older adults. *Journal of interpersonal violence*. 2001;16(10):1008-1027.

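### The completion code shows each youth their own suicide-risk score on a 1-to-5 scale, and two of three intervention surveys fall in group sessions with no private hand-over described, so the aim that it goes unnoticed is poorly protected

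*Protocol*

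**What the plan says.** The procedure is in the Protocol, under the additional protocol for identifying suicidality in survey participants; the combined protocol and SAP does not contain it. The survey is "programmed to include the youth's score on the suicide measures" on its final screen, next to the completion message. The lowest number, 1, means no risk and the highest, 5, means highest risk. Codes 2 to 4 are not defined. The same screen tells the youth: "Let the research team know you've finished the survey to receive your gift card". Of the number, the plan says "This code is designed to not catch the attention of the student", while staff are to read the risk level from it. Staff then refer the youth to the school counselor, confidentially and away from the group session.

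The setting is given elsewhere in the Protocol:

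- 10-week P&E Intervention Procedures: "The 10-week protocol includes an introductory and data collection session", and the last of the ten sessions is also used for data collection. The combined document says the same.
- Participants, Limitations: "we will limit the individual-level intervention group size to 12".
- LGBTQ Youth Procedures: surveys take place in September, November and May, and youth fill them in themselves on tablets, laptops or phones. The same section adds "School staff will not have access to participant data from surveys", a sentence that also appears in the combined document.
- Proud & Empowered! Intervention: control-school youth complete the surveys at the same three time points. Where and how they do so is not described.

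**The concern.** The code has two jobs that pull against each other. Staff must be able to read a risk level from it, and the youth must not notice that it means anything. A number that rises with risk serves the first job well and the second badly, especially when schoolmates finish the same survey in the same room and may find that their numbers differ. If the same scale returns at each wave, a youth can also compare their own numbers over time.

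Three things are at stake:

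- **Privacy.** The Protocol lists unintended release of confidential information among its five foreseeable sources of adverse events, and it waives signed consent because of the privacy risks this group faces. Suicide-risk level is among the most sensitive items collected.
- **Screening.** A youth who has worked out the number could avoid a high one at the next wave, which weakens the check that the procedure exists to provide.
- **Measurement.** Suicidality is one of the named behavioral health outcomes. If answers change because the code has been understood, the follow-up data carry that change.

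**Working it through.** The plan states no figure on this point, so there is none to reproduce. The check is mainly a comparison of sections.

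**1. Does the code carry an order?** The ends are defined (1 none, 5 highest) and the number is described as the score. The order of codes 2 to 4 is therefore implied, though not spelled out.

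**2. How many surveys fall in a shared session?** There are three time points. The first of the ten weekly sessions holds the September survey and the last holds the November survey. That is 2 of 3 for intervention youth. The code section itself speaks of help given outside the intervention session, which fits surveys being completed inside it. The May setting is not stated.

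**3. What protects the code in that setting?** Self-administration on a device gives some privacy while answering. The confidential referral protects the step after staff have read the code. Nothing covers seating, who can see the final screen, how the code passes from youth to staff, or whether the mapping changes between waves.

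**4. Would codes differ within a group?** This is illustration only, because the documents give no rate. Let p be the share of youth with a code above 1, taken as independent between youth. The chance that a group of 12 has at least one such youth is 1 − (1 − p)^12:

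- p = 0.10: 1 − 0.90^12 = 0.718
- p = 0.20: 1 − 0.80^12 = 0.931
- p = 0.30: 1 − 0.70^12 = 0.986

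Subtracting p^12, for the case where all 12 are above 1, leaves these values unchanged to three decimals. They are lower bounds on the chance that a group holds at least two different codes. They say that differing codes would be usual under these assumptions. They are not the chance that anyone sees, compares or decodes a number.

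**5. Can an effect on the arm comparison be sized?** Treat reported risk as yes/no, and let u_I and u_C be the shares of at-risk youth who stop reporting at follow-up in the intervention and control arms. With no true effect, the spurious difference is p × (u_I − u_C). For p = 0.20 and u_I = 0.20 it is 0.20 × 0.20 = 4.0 percentage points if u_C = 0, and zero if u_C = 0.20. The documents give none of p, u_I or u_C. They also give no yes/no definition of suicidality: the measure has six items, and the analysis named is a cluster-randomized repeated measures ANOVA. The result depends wholly on what is assumed.

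**The case against.** The strongest reply is that exposure is possible but not documented. Youth are told to report that they have finished. Nothing says that the number is spoken aloud, and staff could read it from the screen. The referral is confidential and away from the group. Counselors also arrange rooms and counseling slips for participants, so being seen with a counselor need not mark anyone as at risk. This stands against any claim that classmates do see or hear the numbers, or that a referral reveals what they mean. It does not answer the narrower point that the plan describes no safeguard for the display or hand-over of the code.

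A reader might also infer that intervention youth would learn to under-report and that the fall would pass for a benefit on suicidality. The documents do not support that. The section first speaks of the surveys of intervention participants and then says that all youth see the final screen, so it is unclear whether control schools use the code. If control youth are also surveyed in groups with the same code, any distortion could be similar in both arms. A range such as 1.0 to 7.5 points (0.10 × 0.10 to 0.30 × 0.25) only multiplies assumed rates and sets control under-reporting to zero.

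Finally, a reader might see a contradiction between the counselor referral and the sentence "School staff will not have access to participant data from surveys". The two can be read together: research staff read the level and make the connection, and nothing says that scores or answers are passed on. A referral does signal concern, so a clarifying sentence is reasonable. The assent and consent forms are not in the material reviewed, so it cannot be said that youth are misinformed.

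**Conclusion.** The concern holds in a limited form. The code shows the youth's own suicide score on an implied ascending scale, two of three intervention surveys take place in groups of up to 12, and neither private hand-over nor a change of code between waves is described. The stated aim that the code should go unnoticed is poorly protected, so a youth's risk level can be exposed or decoded, and later answers and screening could be affected.

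This conclusion rests on the text of the Protocol and on its silence about hand-over, not on evidence that exposure has occurred. The size of any effect cannot be given. Bias between arms is an open question until the control and May settings, and the use of the code in control schools, are stated. The case for change is that a sensitive item can be protected better at low cost.

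**What to change.** Replace the ordered 1-to-5 display with completion codes that have no order:

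- Give each risk level several codes, have the survey assign one at completion, and change the set at each wave. Staff read the level from a list that only they hold. A code fixed for each student in advance would not work, because the level is known only when the survey ends.
- Use the same scheme in all arms, and state plainly whether control-school youth see a code.
- Describe the survey setting in both arms and at all three waves, including screen privacy and a private hand-over of the code.
- Write down what codes 2 to 4 stand for under the existing scoring.
- Leave the referral procedure as it is.
- Add a sentence in the Protocol and the combined document explaining how the statement on school staff and survey data fits with the counselor referral.

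The cost is survey reprogramming, a code list for each wave and some staff training. The downside is a small risk of look-up error, which could misstate a youth's level, so training should cover use of the list. The change does not stop a youth from drawing conclusions from the referral itself; it addresses only the display and hand-over of the code.

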Study Title: Efficacy of a Multi-level School Intervention for LGBTQ Youth**Study Procedures****Background**

Sexual and gender minority (SGM; e.g., lesbian, gay, bisexual, transgender, queer) adolescents experience victimization in schools at much higher rates than their peers. Studies, including meta-analyses, have found that gay and lesbian students are 8 to 10 times more likely to be victimized in school than heterosexuals, with rates even higher among transgender youth. Victimization comes from not only other students but also teachers and administrators. This bias-based victimization, part of what is commonly known as minority stress, has been associated with poor behavioral health outcomes for SGM adolescents. This includes disparate rates of depression, anxiety, self-harm, and suicidal ideation and attempt in sexual minority adolescents, with even stronger disparities found among gender minority adolescents. Even compared to similarly victimized non-SGM peers, victimized SGM adolescents report significantly higher rates of suicidality.

Studies also indicate that SGM victimization is more common in schools that lack protective policies and resources such as gender/sexuality alliances (GSAs), SGM-specific antibullying policies, teacher/staff training, and openly supportive allies. When schools lack SGM bullying policies, SGM students are more likely to report suicidality than peers in schools with these policies. We assert that any intervention for SGM youth must simultaneously (a) help SGM youth cope with minority stress and (b) work to reduce the likelihood of future victimization by addressing school-level factors. Thus, it is concerning that a recent review found there are no determinative studies, such as RCTs, of the efficacy of school-based interventions for SGM youth.

Objectives

To fill this gap, we have developed a first-of-its-kind school-based intervention for SGM youth, *Proud & Empowered!* (P&E). The multi-level program was developed over the last 9 years through (a) psychometric, developmental, and acceptability studies funded by the NIH, foundations (Zumberge), and intramural sources; (b) a collaboration with three SGM youth drop-in centers, more than 100 SGM youth, and a dozen academic and clinical experts; and (c) an exploratory study (R21MD013971) to assess the feasibility and preliminary efficacy of the intervention. Given encouraging findings, we now propose to employ a large-scale randomized controlled trial (RCT) with 24 schools in Los Angeles to establish program efficacy. At intervention sites ($n = 12$), after the 10-session small group portion of the intervention with SGM youth is completed, peer allies (who are identified through a popular opinion leader model) are invited to participate in 4-session leadership program focused on changing SGM-related school climate. This is followed by student-led implementation of environmental change strategies at the school level focused on key domains of school climate described by

Thapa et al. (2013): safety, relationships, teaching and learning, and institutional environment. At the SGM student level, analysis will focus on the hypothesized mechanism of change (minority stress) and key behavioral health outcomes (depression, anxiety, PTSD, suicidality, substance use).

Change in school climate will also be assessed qualitatively using content analysis and observational methods in the intervention and post-intervention years. Our specific aims are to: 1) Determine participant-level efficacy of the intervention in an RCT with 24 schools, 2) Determine the schoolwide intervention effects on (a) reporting of minority stress and behavioral health outcomes among all SGM students and (b) perceptions of school climate (norms, attitudes, beliefs, bullying behaviors toward SGM youth, policies) among all students, and 3) Examine factors that may affect intervention success (e.g., fidelity of implementation, barriers or facilitators to implementation, school or student characteristics) to prepare the intervention for future dissemination.

Participants

1. Inclusion Criteria:

a) P&E Intervention Participants will be eligible to participate if they: 1) are students at the selected schools, 2) self-identify as lesbian, gay, bisexual, transgender, or any other non-heterosexual/cisgender identity, 3) speak English, and 4) are able and willing to provide assent/consent.

b) POL Allies/Make Space Participants will be eligible to participate if they: 1) are selected by the student body as a popular opinion leader (i.e. students who others look up to and consider good leaders), 2) are willing to be an ally to the LGBTQ community, and 3) are able and willing to provide assent/consent.

2. Exclusion Criteria: not meeting the inclusion criteria above

3. Special Population:

a) Minors: a waiver of parental permission for youth participation has been granted as there is concern that an IRB requirement of parental permission will put some sexual minority youth at risk regarding disclosure of their sexual orientation to their parents. This may then place these youth at risk for parental harassment, abuse, or expulsion from the parental home.

b) Pregnant Women: There is no risk to pregnant individuals due to participation. Therefore, we will allow those who are pregnant to participate in the study.

4. Limitations:

a) Although our feasibility trial had one school with 17 youth participating in the Proud groups, we found that this group was too large to manage effectively, and so we will limit the individual-level intervention group size to 12.

b) Given that this is a Los Angeles-based study with a limited budget and that the majority of schools in the Greater Los Angeles Area are English speaking, we will be restricting enrollment those who speak English.

Recruitment

LGBTQ Cohort: Students will be asked in the schoolwide Popular Opinion Leader (POL) survey (administered at the start of the school year) if they would be interested in hearing more about an intervention to improve the mental health of LGBTQ+ youth. Students who endorse interest will receive a short description of the study and if interested, can add their names to the subject pool. Youth will be told that if selected to participate in the program they will be contacted by Study Coordinator ([name]). In week three of the school year, we will randomly select 12 names at each school from the LGBTQ+ youth identified via these recruitment methods to be invited to participate in the LGBTQ+ youth cohort portion of the study.

POL Allies: To identify POL allies, we adapt methods used successfully in school-based anti-smoking campaigns. That is, the school wide surveys will also ask students to list the names of five students in their school who they “respect,” “look up to” and “consider good leaders”. The top twenty nominated students (POLs) will be contacted by Study Coordinator and screened for interest in participating in the school climate portion of the program. Other than the biostatistician, PI and Study Coordinator, no one will know the identity of these twenty individuals. This screening will assess for the student’s willingness to operate as an effective LGBTQ ally (e.g., willingness to provide visible support for SGM students), and students who are not interested, for any reason (related to topic or otherwise), will not be asked to participate. After screening each POL for interest in participation, Study Coordinator will then randomly select ten of the students identified to participate in the school-wide intervention portion of the study.

Methods

Proud & Empowered! Intervention: The proposed study is intended to rigorously test the efficacy of Proud & Empowered! (P&E) program in a large-scale RCT with 24 high schools across the Greater Los Angeles Area. Schools will be randomly assigned to an intervention or control condition. LGBTQ participants in the intervention schools will participate in P&E, whereas those attending control schools will complete only study survey measures during the study on the same timeline (all three time points) as the intervention schools.

LGBTQ Youth Procedures: For LGBTQ P&E participants, **measures (information on measures can be found in the *Instrumentation* section below) will be obtained at three time points: the beginning of the P&E intervention (September), after the intervention period (November), and at the conclusion of the school year (May).** LGBTQ+ youth participants will create a Unique ID that study team will use to link measures taken over time. Detailed information on

recruitment of LGBTQ youth participants can be found in the *Recruitment* section above. Names of LGBTQ youth participants who opt-in to participation will be shared with a school counselor. School counselor will ensure there is a time and space available for each student to meet for a 45-minute intervention session once per week for 10 weeks. The study activities will occur at the school during school hours and the school counselor will ensure students can discreetly participate in the intervention sessions by either 1) grouping participating youth into the same homeroom/advisory period where the intervention will administered by Study Facilitator/Study Coordinator, or 2) providing students with a counseling slip, allowing them to miss a class to participate in the intervention session. Schools will choose what works best for them. If option 2 is selected, intervention sessions will be staggered and run during a different class period each week so that participating youth do not miss the same class every week. USC study staff ([name], [name]) will present adolescents with information sheets/assent, or informed consent from those aged 18 or older, and obtain verbal assent/consent in order to keep as little identifying information about LGBTQ+ participants as possible. Next, each LGBTQ participant will create a unique identification code that will be used in the participant's survey entries to link successive data points. Surveys will be self-administered on tablets, laptops, or cell phones. The data manager ([name]) and study facilitator at the study site will track participant names and unique identifiers to keep track of the number of sessions attended by students (dosage). School staff will not have access to participant data from surveys. Youth who turn 18 during the study will complete an informed consent.

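### Youth at all 24 schools are recruited with program-framed wording although control youth complete surveys only, so disappointed control answers could mimic a benefit and uneven refusal could bias the comparison either way

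*Combined protocol and SAP*

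**What the plan says.** **Combined protocol and SAP, Recruitment (LGBTQ Cohort).** A schoolwide survey asks students "if they would be interested in hearing more about an intervention to improve the mental health of LGBTQ+ youth". On what follows, the text says: "Students who endorse interest will receive a short description of the study and if interested, can add their names to the subject pool". Then: "Youth will be told that if selected to participate in the program they will be contacted by Study Coordinator". The team will "randomly select 12 names at each school". No separate wording for control schools is given.

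**Combined protocol and SAP, Methods (Proud & Empowered! Intervention).** Schools are randomised, and "those attending control schools will complete only study survey measures during the study".

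**Protocol dated August 23, 2023, Recruitment (LGBTQ Cohort).** Flyers and counselors replace the survey question, and the sentence about being selected for the program is gone. Twelve names are still drawn at each school. Those youth are invited to a first P&E session, where they receive the link to the Proud & Empowered e-consent. Methods in this document also gives control youth surveys only, at three time points.

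**Both documents.** Surveys are self-administered. The Data Analysis sections plan a cluster-randomized repeated measures ANOVA of the participating cohort against its control-school counterparts. They describe no check on differential refusal and no missing-data method. No attention control, wait-list offer or blinding is described. The timing of school randomisation relative to recruitment and consent is not stated.

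**The concern.** Recruitment is framed around the program at schools where no program will be offered. Youth who come forward for a mental-health intervention and then receive only questionnaires have a reason for disappointment that intervention youth do not share. This could act in two ways:

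- **Answers.** Control youth may report worse mood or stress at later waves. With self-reported outcomes, this looks like a program benefit.
- **Refusal and dropout.** If the arms lose different kinds of youth, the two cohorts are no longer comparable. The direction depends on who leaves.

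At stake is the participant-level efficacy comparison (Aim 1), because nothing described in the plan would prevent or detect either effect.

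**Working it through.** **No figure to reproduce.** The documents give no alpha, power, SD, ICC, effect size or dropout rate. What follows is an illustration under stated assumptions.

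**Inputs from the documents.** There are 24 schools, of which 12 are intervention sites (Objectives), so 12 are controls by subtraction. Twelve youth are invited per school: 24 x 12 = 288 in total, 144 per arm.

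**Assumed.** Two-sided alpha 0.05; SD 1; ICC 0.02 to 0.10; true effect zero; control answers worse by b = 0.1 or 0.2 SD; all invited youth analysed.

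**Step 1: standard error without baseline adjustment.** SE = sqrt(2 x (1 + 11 x ICC) / 144).

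- ICC 0.02: sqrt(2 x 1.22 / 144) = 0.130
- ICC 0.10: sqrt(2 x 2.10 / 144) = 0.171

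**Step 2: chance of a significant result.** This uses a noncentral t with 24 - 2 = 22 df, noncentrality b / SE and critical value 2.074, counting both tails.

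| ICC | b | b / SE | Significant |
|---|---|---|---|
| 0.02 | 0.1 | 0.77 | 11.4% |
| 0.10 | 0.1 | 0.59 | 8.7% |
| 0.02 | 0.2 | 1.54 | 31.2% |
| 0.10 | 0.2 | 1.17 | 20.2% |

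Against a nominal 5%, this is about 9-11% for 0.1 SD and 20-31% for 0.2 SD. Almost all of the excess lies on the benefit side.

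**Step 3: what baseline adjustment does.** Assume a baseline correlation of 0.6. The SE is multiplied by sqrt(1 - 0.36) = 0.8, so at ICC 0.02 it becomes 0.104.

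- *Shift arises only after September.* The full shift remains and precision is better: 15.1% for 0.1 SD and 45.1% for 0.2 SD.
- *Shift equally present in September.* The remaining shift is b x (1 - 0.6), that is 0.04 or 0.08 SD: 6.6% and 11.4%.
- *Pure change-from-baseline contrast.* An equal shift at baseline and follow-up cancels.

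**Step 4: refusal.** Let r be the excess refusal in control schools and D the mean distress of refusers minus that of those who stay. The control mean moves by -r x D. With r of 0.10 to 0.30 and an absolute D of 0.25 to 0.5 SD (both assumed), the size runs from 0.10 x 0.25 = 0.025 to 0.30 x 0.5 = 0.15 SD. If the refusers are the more distressed, the remaining controls look better and a benefit is hidden. If they are the less distressed, controls look worse and a benefit is mimicked.

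**The case against.** **The message may not mislead.** A reader might infer that control youth are told something untrue. The documents do not establish that. The sentence is conditional on selection; youth get a short study description before joining the pool; and information or assent comes before any survey. None of those texts is shown, and any of them may disclose a survey-only arm. This stands. Even so, the interest question comes before the description, and the plan's own account of what youth will be told speaks only of the program.

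**Refusal need not be one-sided.** It is tempting to say that refusal and disappointment arise only in control schools. The documents give no refusal data. Intervention youth can also decline: they face ten weekly sessions, possible missed classes and a risk of being outed or targeted. Survey completers receive a gift card (Protocol, suicidality protocol for survey participants), which encourages control youth to stay. This stands too.

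**The quoted sentence is not in the dated protocol.** Correct, but the uniform invitation to a first P&E session there carries the same framing, with controls still on surveys only.

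**Baseline may absorb the shift.** Youth may learn their condition before the September survey, in which case repeated measures would remove part or all of it. This is a fair limit on the size, as Step 3 shows, but the plan does not say when youth learn their condition.

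**Conclusion.** The concern holds as a correctable weakness in recruitment wording, present in both documents. Program-framed recruitment at every school, a survey-only control, self-reported outcomes and no described safeguard leave room for disappointed control answers to mimic a benefit.

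Without baseline adjustment, false significance rises from 5% to about 9-11% for an assumed 0.1 SD shift, and to about 20-31% for 0.2 SD. These figures rest on assumed shifts, ICC 0.02 to 0.10 and full participation.

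Two stronger conclusions are not supported. The first is that the risk reaches 15% or 45%: that requires baseline adjustment together with a shift absent in September, and the figures fall to about 7% and 11% if the shift is already there. The second is that refusal points to a false benefit: its direction is unknown, and if the more distressed control youth decline, it hides one.

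**What to change.** Use one condition-neutral text at all 24 schools, in the Recruitment sections of both documents:

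- Describe a study of LGBTQ+ student wellbeing with three surveys, in which some schools also hold a weekly group.
- In the combined document, refer to being selected for the study rather than for the program, and replace the interest question about an intervention.
- In the dated protocol, replace the uniform invitation to a first P&E session with an invitation to a first study survey visit. Session one of the 10-week program already includes data collection, so this description is accurate in both arms.
- Report the numbers invited, assented and surveyed at each wave, by arm.

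**Cost.** A minor IRB amendment to the survey question, script and invitation. Interest may be slightly lower when the group is not promised. The change lowers the risk but does not remove it: youth in an unblinded survey-only arm will still know that other schools have a group.
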